12. STUDY ENDPOINTS AND MEASUREMENTS

12.1. Efficacy Assessments

The following efficacy measurements will be conducted at the times specified after the end of surgery:

- Pain intensity scores using the NRS-R at baseline (prior to the nerve block) and 2, 4, 8, 12, 24, 36, 48, 60, and 72 hours, and at first request for rescue pain medication ([Appendix 1](#)).
- Pain intensity scores using the NRS-A (where the prescribed activity is actively flexing the involved knee up to 45 degrees) at baseline (prior to the nerve block) and 2, 4, 8, 12, 24, 36, 48, 60, and 72 hours, and at first request for rescue pain medication ([Appendix 1](#)).
- Time of first opioid rescue.
- Opioid use.
- Conventional bupivacaine HCl use.
- Sensory function assessment (i.e., cold test) at baseline, when the subject wakes up after surgery (general surgery subjects only), and at 2, 4, 12, 24, 36, 48, 60, and 72 hours after surgery, or until the subject's sensitivity to cold is demonstrated on two consecutive evaluations.
- Overall benefit of analgesia score questionnaire at 24, 48, and 72 hours ([Appendix 3](#)).
- Subject satisfaction with postsurgical pain control at 72 hours and Day 30 using a 5-point Likert scale ([Appendix 4](#)).
- Predefined treatment-emergent opioid-related AEs at 72 hours following surgery during Part 1 only ([Appendix 6](#)).

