5. DEFINITIONS

The terms study site and center are used interchangeably.

Time 0 is defined as the start time of study drug administration for the PK analyses, and as the end time of surgery for the efficacy analyses.

Study day: Day 1 is defined as the day study drug is administered. Positive study days will be measured forward in time from Day 1, with Day 2 being the calendar day immediately following the day study drug is administered. Day -1 is the calendar day immediately preceding the day study drug is administered and negative study days will be measured backward from Day -1.

Study visits and time points will be determined from the scheduled times as reported on the electronic CRFs (eCRFs) for the summarization and analysis of data that are shown by time point, unless otherwise specified.

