- If the year is unknown, then the date will not be imputed and will be assigned a missing value.
- If the month is unknown, then:
 - i) If the year matches the year of the dose of study drug date, then the month and day of the dose of study drug date will be imputed.
 - ii) Otherwise, 'January' will be assigned.
- If the day is unknown, then:
 - i) If the month and year match the month and year of the dose of study drug date, then the day of the dose of study drug date will be imputed.
 - ii) Otherwise, '01' will be assigned.
- If the time is unknown, then:
 - i) If the date (day, month, and year) match the date of the dose of study drug date, then the time of the dose of study drug time will be imputed.
 - ii) Otherwise, "00" will be assigned.

For partial stop date/time:

- If the year is unknown, then the date will not be imputed and will be assigned a missing value.
- If the month is unknown, then 'December' will be assigned.
- If the day is unknown, then the last day of the month will be assigned.
- If the time is unknown, then the last time of the day will be assigned.

If the above rules for stop dates result in an illogical date with regards to the dates the subject is in the study, then the stop date will be replaced with the subject's date of completion/ withdrawal. Further, should the above rules not result in the most conservative date, then the imputed value may be replaced by a date that will lead to a more conservative analysis. Should this situation arise, specific details will be provided in the derived dataset specification documentation or documented in the derived analysis data set program using comments.

AE Severity or Relationship to Study Drug

If severity of an AE is not reported, then for tables of AEs by severity, the event will be classified as 'Severe'. If relationship to study drug is not reported for an AE, then for tables of study-drug related AEs, the event will be classified as related.

Time to Event Time

For calculating time to an event when only the hour, and not the minutes, are reported for the time of the event, then the minutes will be set to zero.

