For the analysis of time to first opioid rescue, time to first opioid rescue will be computed in hours as the date/time of the first opioid rescue minus the date/time of the end of surgery. If a subject is not administered an opioid, the time to first administration will be censored at 72 hours after surgery or at the time of last follow-up, whichever is earliest. Time of last follow-up will be defined as the later of (1) the last pain assessment, (2) the start time of the last rescue or concomitant medication, or (3) the start time of the last AE.

Time to first opioid rescue will be analyzed by the Kaplan-Meier method. The n (%) of subjects administered an opioid as well as the n (%) of censored observations will be presented for each treatment group. In addition, Kaplan-Meier estimates in terms of the median and its 95% CI, and the 25th and 75th percentiles will be presented for each treatment. Log-rank tests will be used to compare each dose of liposome bupivacaine (Part 1) and the one dose of liposome bupivacaine (Part 2) to placebo.

For Part 2, the efficacy measures will be analyzed using a hierarchical fixed-sequence stepwise testing procedure. To protect the Type 1 error rate, the testing will be performed in a sequentially rejective fashion. First, the total postsurgical opioid consumption through 72 hours will be tested. If the test of opioid consumption is significant at the two-sided 0.05 level then, and only then, the time to first opioid rescue will be tested. Each test will be declared positive at the two-sided 0.05 significance level.

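### The minutes-to-zero rule in SAP 7.1.3 has no floor at the end of surgery, so an early opioid rescue recorded only to the hour can get a negative time

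*SAP*

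**What the plan says.** Under the sub-heading on time to event in SAP 7.1.3, the rule for a partly recorded time is that "when only the hour, and not the minutes, are reported for the time of the event, then the minutes will be set to zero". It is worded as mandatory and has no lower bound or exception.

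SAP 7.6.2.2 defines time to first opioid rescue as "computed in hours as the date/time of the first opioid rescue minus the date/time of the end of surgery". SAP 5 sets Time 0 "as the end time of surgery for the efficacy analyses". The analysis follows in 7.6.2.2: "Time to first opioid rescue will be analyzed by the Kaplan-Meier method", with a log-rank test against placebo. The censoring rule there, "the time to first administration will be censored at 72 hours after surgery or at the time of last follow-up, whichever is earliest", applies only to subjects who receive no opioid.

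Two other provisions in SAP 7.1.3 bear on the point. Missing surgery or rescue information that cannot be recovered by query may be imputed case by case, conservatively. The worked example there places a Day 1 pain medication with no recorded time at the end of surgery.

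**The concern.** The hour-only rule always moves an event earlier, and nothing stops it moving the event past the time origin. A rescue in the same clock hour as the end of surgery is then placed before surgery ended, which is impossible for a postsurgical rescue. The SAP is also uneven here. A Day 1 rescue with no time at all gets a valid value of 0, while one whose hour is known can get an invalid negative value.

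The endpoint is the second of the two secondary endpoints in the Part 2 fixed sequence, tested at two-sided 0.05. Because the SAP is silent on negative times, someone would have to choose how to handle them after seeing the records. If the choice were to drop them, the loss would fall only on subjects rescued in the first hour and would be larger in the arm rescued earlier. Placebo is a saline block, so that arm is expected to be placebo, and the loss would tend to narrow the apparent difference.

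**Working it through.** The documents give no figure on this point to reproduce. The check is arithmetic on the stated rule, followed by an illustration on assumed inputs.

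**Inputs from the documents.** Minutes set to zero (SAP 7.1.3); time = rescue minus end of surgery (SAP 7.6.2.2); 90 per arm in Part 2 (SAP 8); two-sided 0.05 (SAP 7.6.2.2).

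**Inputs assumed.** End-of-surgery minute uniform over 0 to 59; share of hour-only records from 2% to 100%; exponential rescue times with the medians shown below; no censoring in the power illustration.

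**Step 1: the imputed value.** Let surgery end m minutes past the hour and the true rescue come t minutes later. Then

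imputed time = 60 × floor((m + t)/60) − m.

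This is negative exactly when m ≥ 1 and m + t ≤ 59.

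- End 10:40, rescue 10:55: 10:00 − 10:40 = −40 min (true +15).
- End 10:05, rescue 10:55: 10:00 − 10:05 = −5 min (true +50).
- End 10:40, rescue 11:05: 11:00 − 10:40 = +20 min (true +25), so not negative.

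**Step 2: how often, given an hour-only record.** P(negative) = (59 − t)/60 for t up to 59 minutes, and 0 beyond.

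| True time to rescue | P(negative) |
|---|---|
| 10 min | 49/60 = 82% |
| 20 min | 39/60 = 65% |
| 30 min | 29/60 = 48% |
| 45 min | 14/60 = 23% |
| 59 min or more | 0% |

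The mean shift for any hour-only record is −(0 + 1 + … + 59)/60 = −29.5 min.

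**Step 3: does other text prevent it?** The censoring rule covers subjects without an opioid, not those with an event. The repair for illogical dates in SAP 7.1.3 concerns stop dates under the adverse-event and concomitant-medication rules. The case-by-case clause is optional and general, whereas the hour-only rule is specific and mandatory. None of these sets a floor.

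**Step 4: expected number of negative times in an arm of 90.** This is 90 × hour-only share × P(negative) averaged over the assumed rescue times.

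| Median rescue time | Average P(negative) | 2% hour-only | 10% | 30% | 100% |
|---|---|---|---|---|---|
| 30 min | 43.9% | 0.8 | 4.0 | 11.9 | 39.5 |
| 120 min | 14.8% | 0.3 | 1.3 | 4.0 | 13.3 |

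**Step 5: effect on the log-rank test.** Simulated power, 90 per arm, 400 runs per row. The standard error of each power is about √(0.85 × 0.15/400) = 1.8 points. Within a row all methods use the same simulated data.

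| Medians (min) | Hour-only | True times | Negatives kept | Floored at 0 | Dropped | Mean negative per arm |
|---|---|---|---|---|---|---|
| 30 vs 48 | 10% | 84.5% | 84.0% | 84.0% | 84.5% | 3.8 vs 3.0 |
| 30 vs 48 | 30% | 84.5% | 83.5% | 83.5% | 82.8% | 11.7 vs 8.4 |
| 30 vs 48 | 100% | 85.5% | 82.2% | 82.5% | 68.0% | 39.3 vs 28.3 |
| 60 vs 96 | 10% | 87.2% | 86.0% | 86.0% | 86.2% | 2.4 vs 1.7 |
| 60 vs 96 | 30% | 86.5% | 86.5% | 86.5% | 84.2% | 7.0 vs 4.9 |
| 60 vs 96 | 100% | 87.5% | 87.0% | 86.5% | 77.8% | 24.2 vs 16.4 |

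The floor leaves no negative times and keeps every event. Its power matches that of keeping the negative values to within half a point, because both leave these subjects among the earliest events. Dropping costs little at 10%, about 2 points at 30%, and 10 points or more only when every record lacks minutes.

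**The case against.** The strongest reply is that this will rarely arise and that the team could deal with it. Protocol 13.5 requires the date, time and amount of every rescue. SAP 7.1.3 expects those times to be complete, relies on queries first, and then allows conservative case-by-case imputation. Protocol 13.1 defines postsurgical as after the end of surgery, so a negative value would be recognised as impossible. This limits the size of the problem. It does not remove it, because the hour-only rule is specific and mandatory and the discretion is only optional.

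A reader might infer that the log-rank analysis cannot run on these subjects, or that they will be dropped. The documents do not support either inference. The log-rank statistic depends only on the order of the times, so a negative value that is kept still ranks as an early event. The SAP never says that negative times are excluded. The dropped-subject results in the working show one possible handling, not the plan.

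A reader might also infer that the rule for untimed Day 1 medication needs the same floor. It already gives the end of surgery.

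Nor is there a case for replacing the zero minutes with the time of the pain score taken "at first request for rescue pain medication" or with the half hour. Request time is not administration time, which is what the endpoint uses. The average shift of 29.5 minutes arises under the same rule in both arms of a 72-hour assessment.

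**Conclusion.** The point holds as a minor defect. Two stated rules together give an impossible value for an hour-only rescue in the same clock hour as the end of surgery (unless surgery ended exactly on the hour), and no text says what to do with it. That the values are negative follows from the SAP alone. How many there are does not: the share of hour-only records and the distribution of rescue times are not in the documents, and every count and power above rests on assumed values.

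At a plausibly low share of hour-only records the effect on the test is negligible. Any loss from dropping would work against finding a difference if placebo is rescued earlier, so a false-positive concern does not follow. The test is also reached only if the primary endpoint and 72-hour opioid consumption are both significant (SAP 7.1.4).

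**What to change.** Add one sentence to the time-to-event rule in SAP 7.1.3: after minutes are set to zero, the event time is never earlier than the end of surgery, so time = max(0, imputed time), and the record stays in the analysis as an event. This agrees with the SAP's own example for an untimed Day 1 rescue. It also covers time to sensitivity to cold, which has the same origin and could go negative only at the wake-up test, since the timed tests start at 2 hours. The minutes-to-zero convention and the Day 1 rule can stay as they are.

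The cost is one sentence and one line of programming, with no new data. It should be in place before the Part 2 blind is broken, so that the handling is not chosen with results in view.

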7.1.4. Multiplicity Adjustments

Part 1

The purpose of Part 1 of the study is to select a dose for use in Part 2. Therefore, no alpha-level adjustments for multiple comparisons between the three doses and placebo will be made.

Part 2

Since no multiple comparisons of the primary efficacy variable will be made, no alpha-adjustments will be made.

Also, since there is only one primary efficacy variable and all other efficacy variables are considered secondary, no alpha-adjustments for the primary response variable will be made.

There are two secondary efficacy variables that will be analyzed using a hierarchical fixed-sequence stepwise testing procedure (See [Section 7.6.1](#)). The two secondary efficacy variables will only be analyzed if the primary efficacy variable is statistically significant at the two-sided 0.05 significance level. To protect the Type 1 error rate, the testing will be performed in a sequentially rejective fashion. First, the total postsurgical opioid consumption through 72 hours will be tested. If the test of opioid consumption is significant at the two-sided 0.05 level then, and only then, the time to first opioid rescue will be tested. Each test will be declared positive at the two-sided 0.05 significance level.

7.1.5. By-Center Analyses

Up to 40 sites/centers will enroll subjects in this study. The primary efficacy results will be summarized by site but site will not be included in any models.

7.2. Subject Disposition

The number and percentage of subjects who are in each analysis set, who completed the study, and who discontinued early from the study, along with reasons for early withdrawal, will be summarized by treatment group and for all subjects, separately for Part 1 and Part 2. In addition, the same summary will be produced by site for Part 2.

7.3. Description of Demographics and Baseline Characteristics

Demographics and baseline characteristics will be summarized by treatment group and for all subjects, separately for Part 1 and Part 2 for the safety analysis set and efficacy analysis set. The variables to be included in the summary are age, gender, ethnicity, race, American Society of Anesthesiologists (ASA) physical status class, height (cm), and weight (kg).

Conversions between units for height and weight will use the following formulas:

Weight (kg) = weight (lb) / 2.2046226

Height (cm) = height (in) / 2.54.

7.4. Prior and Concomitant Medication

Prior and concomitant medications will be coded using the World Health Organization Drug Dictionary (WHO-DD) and will be classified according to the default anatomical therapeutic chemical (ATC) classification system code and preferred term.

Prior medications are defined as medications with a stop date/time prior to study drug administration. Concomitant medications are defined as medications taken after the start of study drug administration (i.e., started prior to the start of study drug administration and continued after or started after the start of study drug administration).

Prior and concomitant medications will be summarized using n (%) of subjects by treatment group and for all subjects and by ATC class and preferred term separately for Part 1 and Part 2 for the safety analysis set. Subjects may have more than one medication per ATC category and preferred term. At each level of subject summarization, a subject will be counted once if he/she reports one or more medications at that level.

The tables of concomitant medications will not include rescue pain medications.

7.5. Measurements of Treatment Compliance

Study drug administration will be summarized by treatment group, separately for Part 1 and Part 2 for the safety analysis set. The variables to be included are duration of injection and volume of study drug administered. Surgery will be summarized by treatment group, separately for Part 1 and Part 2 for the efficacy analysis set. The variables to be included in the summary are length of surgery (end time minus start time, in minutes), type of anesthesia, and incision length.

7.6. Efficacy Analysis

All summaries of the efficacy variables will use the efficacy analysis set, which will be based on randomized treatment, and will be summarized separately for Part 1 and Part 2.

7.6.1. Efficacy Variables

The primary efficacy variable is the AUC of the NRS-R pain intensity scores through 72 hours.

Secondary efficacy variables are:

- Total postsurgical opioid consumption (in mg) through 72 hours.
- Time to first opioid rescue.

Tertiary efficacy variables are (the order of these variables has been changed from the order in the protocol to reflect how they will be discussed in the CSR):

- The NRS-R and NRS-A pain intensity scores at each assessed time point.
- The AUC of the NRS-R pain intensity scores through 24, 36, 48, and 60 hours.

- The AUC of the NRS-A pain intensity scores through 24, 36, 48, 60, and 72 hours.
- The AUC of the NRS-R pain intensity scores from 24-48 and 48-72 hours.
- Proportion of subjects who are pain free (defined as an NRS pain intensity score of 0 or 1) at each assessed time point.
- Total postsurgical opioid consumption (in mg) through 24, 36, 48, and 60 hours.
- Proportion of subjects who receive the following rescue medication(s):
 - Subjects who receive no rescue medications (i.e., opioid or conventional bupivacaine HCl).
 - Subjects who only receive IV hydromorphone bolus.
 - Subjects who receive IV hydromorphone bolus and a second opioid medication.
 - Subjects who receive IV hydromorphone bolus, a second opioid medication, and conventional bupivacaine HCl.
- Overall benefit of analgesia score questionnaire at 24, 48, and 72 hours.
- Subject satisfaction with postsurgical pain control at 72 hours and Day 30.
- Time to sensitivity to cold (listed in the protocol as proportion of subjects at each time point with sensitivity to cold on one of the dermatomes).
- Incidence of predefined treatment-emergent ORAEs (diffuse pruritus, overt respiratory depression, urinary retention as measured by need for postsurgical bladder catheterization, constipation, sedation, confusion, delirium, vomiting, or need for antiemetic medication) at 72 hours (Part 1 only).

7.6.2. Methods of Analysis

7.6.2.1 Primary Efficacy Variable

The primary efficacy variable is the AUC of the NRS-R pain intensity scores through 72 hours using the wWOCF + LOCF imputation method described in [Section 7.1.2](#).

Each dose of liposome bupivacaine (Part 1) and the one dose of liposome bupivacaine (Part 2) will be compared to placebo using analysis of covariance (ANCOVA) with treatment as the main effect and the baseline NRS-R pain intensity score as the covariate. Based on the model, the least squares (LS) means, LS mean difference between the two treatment groups, 95% CI for the LS mean difference(s) between liposome bupivacaine and placebo, and p-value will be reported.

For Part 2, descriptive statistics of the primary efficacy variable will also be shown by site.

Sensitivity Analyses of the Primary Efficacy Variable

For Part 2 a sensitivity analysis will be performed.

The sensitivity analysis will exclude subjects who had interval data for opioid consumption.

7.6.2.2 Secondary Efficacy Variables

The secondary efficacy variables for this study are:

- Total postsurgical opioid consumption through 72 hours.
- Time to first opioid rescue.

For total postsurgical opioid consumption, opioid medications will be converted to a morphine equivalent amount (see the table below). The converted amounts will be totaled for each subject and used in the analysis. When fentanyl is given transdermally the total amount, prior to conversion, will be calculated as the start date/time of administration until the end date/time of administration or end date/time of 72 hours after surgery, whichever is sooner, multiplied by the dose. Projected amounts, for subjects who discontinue early, will be calculated as described in [Section 7.1.3](#).

Medication	Unit	Route	Conversion (Multiplication) Factor
Oxycodone	mg	PO	0.5
Oxycontin	mg	PO	0.5
Morphine	mg	IV	1
Hydromorphone (Dilaudid)	mg	IV	6.7
Hydromorphone (Dilaudid)	mg	PO	1.3
Fentanyl	mcg	IV	0.1
Fentanyl	mcg	Transdermal	0.5
Hydrocodone	mg	PO	0.33

IV = intravenous; PO = oral.

If unplanned rescue medications are administered, then the conversion factor will be determined post-hoc prior to breaking the blind. If a combination opioid is administered then the opioid portion of the medication will be converted and included in the calculations. Opioids given postsurgically with an indication like ‘anesthesia maintenance’ will not be included in the calculation of total opioids.

Prior to analysis, the natural logarithm transformation will be applied to the total amount. When total amount of opioids used is 0, the result will be changed to the lesser of 1 or 0.5 of the smallest total amount observed in the study prior to being transformed with the natural logarithm. To test for significant differences between each liposome bupivacaine dose and placebo (Part 1) and between the one liposome bupivacaine dose and placebo (Part 2), an analysis of variance (ANOVA) with treatment as the main effect will be used. Based on the

model, the LS means, LS mean difference between the two treatment groups, 95% CI for the LS mean difference(s) between liposome bupivacaine and placebo, and p-value will be reported.

For the analysis of time to first opioid rescue, time to first opioid rescue will be computed in hours as the date/time of the first opioid rescue minus the date/time of the end of surgery. If a subject is not administered an opioid, the time to first administration will be censored at 72 hours after surgery or at the time of last follow-up, whichever is earliest. Time of last follow-up will be defined as the later of (1) the last pain assessment, (2) the start time of the last rescue or concomitant medication, or (3) the start time of the last AE.

Time to first opioid rescue will be analyzed by the Kaplan-Meier method. The n (%) of subjects administered an opioid as well as the n (%) of censored observations will be presented for each treatment group. In addition, Kaplan-Meier estimates in terms of the median and its 95% CI, and the 25th and 75th percentiles will be presented for each treatment. Log-rank tests will be used to compare each dose of liposome bupivacaine (Part 1) and the one dose of liposome bupivacaine (Part 2) to placebo.

For Part 2, the efficacy measures will be analyzed using a hierarchical fixed-sequence stepwise testing procedure. To protect the Type 1 error rate, the testing will be performed in a sequentially rejective fashion. First, the total postsurgical opioid consumption through 72 hours will be tested. If the test of opioid consumption is significant at the two-sided 0.05 level then, and only then, the time to first opioid rescue will be tested. Each test will be declared positive at the two-sided 0.05 significance level.

